## Handling of remaining intercurrent events:

- Treatment discontinuations for lack of efficacy or adverse event: consider as non-responder
- Treatment discontinuations for any other reason: set data after discontinuation to be missing

The summary measure: difference in response rates between ZPL389 and placebo.

This estimand differs from that intended by the protocol in that the definition of the endpoint of IGA response has changed to include any use of confounding medication as a non-response, rather than only confounding medication that was adjudicated as having an effect on the IGA response, as specified in the protocol. This change was made following the interim analysis where it was established that handling use of confounding medication did not affect the overall conclusions and so it was decided not to perform the adjudication.

# 2.5.2 Statistical hypothesis, model, and method of analysis

The key questions to address this objective are

- Is there a dose-response relationship for IGA response after 16 weeks of treatment?
- What is the form of this dose-response?

• What doses deliver sufficient efficacy in terms of IGA response after 16 weeks of treatment?

Results from the interim analysis indicate that there is no dose-response relationship and therefore the second and third questions are no longer relevant. Thus the analysis of the primary variable will focus only on the logistic regression analysis described in the protocol, establishing the presence or absence of a dose-response relationship. The MCP-Mod procedure as outlined in the protocol will not be carried out.

The primary objective will be achieved if the null hypothesis of no difference between treatment groups is rejected at 5% one-sided level.

A logistic regression model will be fitted with IGA response as the outcome variable and treatment (dose as categorical variable) and baseline IGA as covariates.

The response  $Y_{ij}$  for subject j in dose group i receiving dose  $d_i$  is modelled as  $Y_{ij} \sim Bin(1, p_{ij})$  with  $p_{ij} = logit^{-1}(\delta_i + \mathbf{x}_{ij}; \boldsymbol{\beta}), i=1,..., 5, j=1,..., n_i$ 

where Bin(1,p) denotes the binomial distribution with parameter 1 and p,  $\delta_i$  is the effect of dose  $d_i$ ,  $\beta$  refers to the vector of regression coefficients corresponding to additional covariates  $x_{ij}$  which represent the baseline IGA category. Finally,  $n_i$  is the number of subjects allocated to each treatment group. If the covariate baseline IGA prevents fitting of a model, it will be dropped.

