For each candidate model a contrast test statistic, based on a linear combination of the treatment estimates per dose will be derived. The contrast coefficients will be chosen to maximize the power to detect the pre-specified candidate models. The global test decision is based on the maximum of the contrast test statistics. A critical value q controlling the type I error rate can be derived from the fact that the contrast test statistics approximately follow a multivariate normal distribution and that their maximum follows the distribution of the maximum of a multivariate normal distribution. If the maximum contrast test statistic exceeds the critical value q, the overall null hypothesis of a constant dose-response curve is rejected and one proceeds to the further estimation steps to determine the dose-response curve and doses achieving target clinical effects using a dose-response model.

Bootstrap model averaging will be used to estimate the dose-response curve, the target dose and to derive confidence intervals. Bootstrap simulation will be performed using the multivariate normal distribution of the estimates of the logit of the response probability for each dose and generalized least-squares fitting of the resulting simulated values (see Pinheiro et al. 2014). The target dose is defined as the dose for which the expected response rate is at least 15% higher than the response rate of placebo which is expected to be about 10%. This will be based on the estimated dose-response curve.

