9.4.3 Handling of missing values/censoring/discontinuations

For efficacy variables based on response (e.g. IGA response, EASI50 response, EASI75 response) missing data will be handled as follows:

1. Subjects with use of confounding therapy as adjudicated will be considered as non-responders after application of the therapy.

2. Subjects who discontinue study treatment permanently or discontinue the study due to lack of efficacy or due to adverse event will be considered as non-responder after discontinuation.

Confidential

3. For subjects who discontinue study or treatment due to other reasons than above or have missing data due to other reasons, missing-at-random will be assumed. The estimates for the logits of the response probabilities as well as the corresponding covariance matrix will be derived applying multiple imputation (MI). The MI model will include IGA categories from all visits from randomization up to Week 16 as well as all EASI score at baseline and absolute change from baseline EASI score for all visits from baseline up to Week 16. For each imputed dataset the logistic regression described in Section 9.4.1 will be performed and results combined for estimation.

For the estimation of the IGA response rates at Week 16 for each treatment group, the estimate for subjects in (3) above will be combined with the non-responders in (1) and (2) above. These combined estimates will be used as input for the MCP-Mod analysis.

If a baseline value is missing, it will be imputed by the mean of the respective treatment group in the respective randomization stratum.

If not stated otherwise, for the secondary

the observed values will be

used for summary statistics, missing values will not be imputed. When doing inference, any missing data will be handled by the respective MMRM model.

For any percent change from baseline analysis, any baseline values equal to zero will be ignored. The total number of zero baseline values will be provided as additional information.

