# 2.6.7 Statistical hypothesis, model, and method of analysis

For all estimands based on binary response rates (e.g. IGA response, EASI50 response, EASI75 response) the simple response rates for each treatment group will be calculated (i.e. number of responders (after imputation as necessary) / the number of subjects in that treatment group.

Differences in response rates between ZPL389 dose groups and placebo will be calculated, and the respective 95% confidence intervals derived using a normal approximation.

For estimands based on continuous data (e.g. percentage change from baseline in EASI, approach will be used. The model will contain treatment group, baseline EASI score, geographical region if possible, baseline IGA score, visit, baseline value\*visit and treatment group\*visit as covariates, and will use an unstructured covariance matrix. Estimates of the mean responses for each visit and treatment group, and of the differences between treatment groups at week 16 will be obtained from this model, together with 95% confience intervals.

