#### Logistic regression

Where logistic regression is specified, the binary outcome variable will be evaluated using a logistic regression model with treatment regimen, baseline IGA, geographical region (if possible).

All p-values reported on linear hypotheses about regression coefficients will be based on the Wald tests from Type III analyses. In the SAS procedure PROC GENMOD, a Type III analysis will be performed by adding the model options: TYPE3, DIST=BIN, and LINK=LOGIT. Logistic regression will be applied to response variables at each visit, and the following steps will be performed:

- 1. Run the PROC GENMOD procedure;
- 2. If convergence not reached, remove the covariates from the model one by one until convergence is reached; start with removing region, followed by baseline IGA;
- 3. If convergence not reached, perform Fisher's exact test.

It should be noted that this model might not converge if response rates are too low.

SAS code for logistic regression:

proc logistic data=aaa;

class TRT STRATA / param=glm;

Model AVAL (event='1') = TRT WEIGHT STRATA;

LSMEANS TRT / diff cl exp ilink;

run;

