## 5.2.3 Multiple imputations for response variables

Where multiple imputation is specified, the missing data will be imputed based on the individual treatment arm information.

Multiple imputation (MI) is a simulation based approach where missing values are replaced by multiple Bayesian draws from the conditional distribution of missing data given the observed data and covariates, creating multiple completed data sets.

Missing values will be imputed simultaneously based on an underlying joint normal distribution and using a Markov Chain Monte Carlo (MCMC) method.

The imputations will be done separately for each treatment group including baseline IGA, geographical region, baseline EASI score as additional covariates.

The number of imputations will be set to 100, the seed for the random function will be set to 3892203 for this study. To generate the multiple imputed data sets, the SAS procedure MI can be used as follows:

The input data set should have one record per subject with baseline EASI score and IGA score as well as the variables to be imputed (e.g. changes from baseline in EASI, or post-baseline IGA score).

Programming notes:

- The SAS procedure MIANALYZE expects a variable called "\_IMPUTATION\_" which is generated by the MI procedure. It might be needed to set the SAS option "VALIDVARNAME=UPCASE" temporarily in the program before the MI call, this option should be reset after the MIANALYZE call to VALIDVARNAME=V6.
- In case there are no missings in one treatment group, the MI procedure does not impute any values. In this case the corresponding data need to be imputed manually outside PROC MI and added to the dataset <impdata>.

The imputed data are saved in data set <impdata>. The outcomes of interest, i.e. the EASI 50/75 response and IGA 0 or 1 response will be calculated, e.g. as follows:

The treatment differences for each imputed data set will then be evaluated by Logistic regression and ODDS ratio as described in Section 5.4.2.2. This analysis will be done by \_IMPUTATION\_ for the comparison to the placebo treatment group. The model should be estimating response probability = 1 by using DESECENDING option. Using the ESTIMATE

option in the GENMOD procedure and the ODS OUTPUT data set "Estimates" provides the estimate for the odds ratio and confidence intervals.

```
PROC GENMOD <option>;
CLASS <stratum> <treatment>;
MODEL <response> = <explanatory variables> / link=logit dist=bin type3;
BY <by-variables);

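### SAP 2.5.2 cancels MCP-Mod but keeps a one-sided 5% success rule for five arms, with no test statistic, contrast or multiplicity rule attached to it

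*SAP*

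**What the plan says.** **Protocol 9.4.2** tests a flat dose-response curve at 5% against a one-sided alternative. Seven candidate shapes each supply a contrast: "The global test decision is based on the maximum of the contrast test statistics". The critical value comes from the multivariate normal distribution of those statistics. Protocol 9.4.3 supplies the input: "The estimates for the logits of the response probabilities as well as the corresponding covariance matrix will be derived applying multiple imputation".

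**SAP 2.5.2** lists three questions: whether there is a dose-response, what form it has, and which doses are effective enough. After the interim it sets aside the second and third, keeps the first, and states: "The MCP-Mod procedure as outlined in the protocol will not be carried out". What remains is a logistic regression with dose as a categorical factor and baseline IGA as covariate. The success rule follows: "The primary objective will be achieved if the null hypothesis of no difference between treatment groups is rejected at 5% one-sided level".

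**Other SAP text that bears on the rule**
- SAP 5.2.2 (Logistic regression): "All p-values reported on linear hypotheses about regression coefficients will be based on the Wald tests from Type III analyses". Fisher's exact test is the last resort if the model does not converge, and the section warns: "It should be noted that this model might not converge if response rates are too low".
- SAP 2.5.1: the summary measure is the difference in response rate between ZPL389 and placebo.
- SAP 5.2.3: each imputed data set is analysed "for the comparison to the placebo treatment group", and a single odds ratio per comparison is pooled.
- SAP 2.6.7: "Differences in response rates between ZPL389 dose groups and placebo will be calculated, and the respective 95% confidence intervals derived using a normal approximation".

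**The concern.** In the protocol, the contrasts give the test its direction, and the critical value for their maximum gives the multiplicity control. The SAP removes both but keeps a rule that needs both. The reason it gives covers curve shape and dose choice, which belong to the modelling step. It does not cover the retained question, which the contrast test was there to answer.

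As written, the rule cannot be executed without choosing a test, and that choice would be made after the interim results were known. At stake is whether the report's statement on the primary objective rests on a test with a known direction, error rate and power.

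**Working it through.** **Inputs.** Placebo rate 10%, maximum effect +20 points, N=360 split 90:45:45:90:90, 90% power at one-sided 2.5% (Protocol 9.8, SAP 3). Seven shapes and the 5% one-sided level (Protocol 9.4.2). Interim count 187 (SAP 1.1). Final N is not stated, so 187 and 360 are both shown. Assumptions: logit scale, no missing data, N=187 split 47/23/23/47/47 in simulation, baseline IGA left out.

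**1. Reproduce the sizing.** Scale each shape so that the logit runs from logit(0.10) = -2.197 to logit(0.30) = -0.847. Arm weight w = n p(1-p). Noncentrality = sum of w × (logit - weighted mean logit)². Weakest shape (ED50 1.85 mg, Hill 3) at N=360:
- rates 10.0, 24.9, 29.8, 30.0, 30.0%
- weights 8.10, 8.42, 9.42, 18.90, 18.90; weighted mean logit -1.054
- noncentrality = 8.10×1.143² + 8.42×0.050² + 9.42×0.198² + 18.90×0.207² + 18.90×0.207² ≈ 12.6

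The maximum-contrast test then has 90.4% power at one-sided 2.5%, which matches the stated 90%. Other scale and variance conventions give about 90-97%. At the 5% level actually used for testing, this minimum is 94.7%. A 4-df Wald test with the same noncentrality has 82.3% power at 5% and 89.3% at 10%.

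**2. Reading (a): Type III Wald test.** The 4 df are inferred from the five-level factor. The 10% level is shown in case one-sided 5% is taken to mean 10% two-sided. Simulation adds 0.5 per cell; the contrast critical value is 2.02.

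| Power over the seven shapes | N=187 | N=360 |
|---|---|---|
| Contrast, one-sided 5%, simulated mean (range) | 84% (82-91%) | 99% (98-99.6%) |
| Wald 5%, simulated mean (range) | 47% (43-58%) | 89% (86-95%) |
| Wald 10%, simulated mean | 64% | 94% |
| Contrast, one-sided 5%, asymptotic range | 74-87% | 95-99% |
| Wald 5%, asymptotic range | 51-65% | 82-92% |
| Wald 10%, asymptotic range | 63-76% | 89-96% |

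*Direction.* Wald rejection at 5% when the two high doses are worse than placebo (assumed true rates, placebo to 50 mg):
- 10/10/10/5/5%: 4% at N=187, 17% at N=360
- 20/20/20/10/10%: 20% and 51%

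The contrast test rejects in under 0.1% of these trials.

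*Type I error*, 10% in all arms (N=187, N=360): Wald 1.2% and 2.2%; contrast 1.9% and 3.3%. Neither is inflated.

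*Where Wald is stronger.* With 30% at 3 mg only or 10 mg only and 10% elsewhere, Wald rejects in 41% (N=187) and 77% (N=360). The contrast test rejects in 0.1-8% and 0.5-19%, depending on the dose and the contrast weighting.

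**3. Reading (b): each dose against placebo, one-sided 5%, any of four.** The correlation between two comparisons is the square root of [n_i/(n_i+n_0)] × [n_j/(n_j+n_0)]. With 45/135 = 1/3 and 90/180 = 1/2, this gives 0.33 (low-low), 0.41 (low-high) and 0.50 (high-high). Independent tests would give 1 - 0.95⁴ = 18.5%. With these correlations the family-wise error is about 15%. Simulation at a 10% rate gives 13.1% (N=187) and 13.7% (N=360).

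**4. Arms with no responders.** If every arm is at 10% and N=187, at least one arm has none with probability 1 - (1-0.9²³)²(1-0.9⁴⁷)³ ≈ 19%. The non-convergence route therefore matters at this size.

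**The case against.** Dropping MCP-Mod is declared and reasoned, after an interim that led to stopping for lack of efficacy. The report is abbreviated and no dose decision hangs on this rule. The Type III sentence is a generic appendix statement, never linked to the success rule. The summary measure and the pooling code point at least as strongly to comparisons with placebo, and nothing shows how to pool a 4-df test over imputations. All of this stands, and it is why two readings are worked through. It does not supply the missing test.

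A reader might infer that the plan, followed literally, declares success on harm. The documents do not support that. The rule says one-sided, so harm counts as success only if that word is set aside to make the Wald test usable. The largest wrong-direction figures also assume a 20% placebo rate, twice the documented one, and nothing in the documents suggests that the drug worsens IGA response. A reader might also infer that the Wald test is weaker in general or inflates type I error. Neither holds: the power loss applies to the seven pre-specified shapes and reverses for an effect at a single low dose.

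**Conclusion.** The gap is real and lies in the text: a one-sided success rule for a five-level factor, with no test attached. Read as a Wald test, it loses direction, and mean power over the candidate shapes falls by about 37 points at N=187 and 10 at N=360 (20 and 5 if run at 10%). The asymptotic calculation gives smaller losses at N=187 but the same ordering for every shape. Read as four placebo comparisons, it carries about 13-15% family-wise error under an any-of-four decision, which the SAP neither states nor rules out.

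The figures rest on the sizing assumptions, complete data and two illustrative sample sizes. Consequences are modest, because the trial had already been stopped and the reported rate differences with intervals would show harm. It should still be corrected, since the SAP sets a formal criterion for the primary objective.

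Minor point: the sample size used one-sided 2.5% while the test is at one-sided 5%, so the stated 90% power is conservative for the contrast test (minimum about 95%).

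**What to change.** In SAP 2.5.2, do one of the following.

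1. **Keep only the multiple-contrast step.** Apply the protocol's seven contrasts to the imputation-combined logits and covariance matrix. Test the maximum one-sided at 5% with the multivariate-normal critical value. Omit curve fitting and the target dose. Label the global p-value and the placebo comparisons descriptive. Name one pre-specified handling of arms with no responders, since a five-arm Fisher test has no direction and the SAP does not say whether its fallback is five-arm or pairwise; the method is the sponsor's choice.
2. **Delete the success rule** and call the analysis descriptive.

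Option 2 costs one sentence. Option 1 costs a short rewording and pooling of five logits with their covariance instead of single odds ratios. Its drawbacks are that the contrast test is conservative at small N (about 1.9% at nominal 5%, N=187) and nearly blind to an effect at one low dose, which is why the global p-value is worth keeping as description. Under either option, add a sentence on the 2.5% sizing level and leave alpha unchanged after the interim.

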# 2.5.3 Handling of missing values/censoring/discontinuations

Where data for IGA response are missing, either because the IGA was not recorded or because the IGA response was set to missing as part of the handling of intercurrent events, the IGA score will be imputed using multiple impuation methods and the IGA response derived from this imputed IGA score.

The multiple imputation model will include IGA categories from all visits from randomization up to Week 16.

For the estimation of the IGA response rates at Week 16 for each treatment group, each imputed dataset for subjects with missing data above will be combined with the non-missing responses for subjects without missing data. For each imputed dataset the logistic regression will be performed and results combined for estimation.

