# **Confounding medications**

Any use of rescue medication or prohibited medication will be considerd as confounding therapy, where rescue medications are collected from the rescue therapy CRF and concomitant medications listed below will be considered as prohibited medications.

- 1. All cases of conmeds in the following ATC classes
  - D07 CORTICOSTEROIDS, DERMATOLOGICAL PREPARATIONS
  - R06A ANTIHISTAMINES for systemic use
- 2. Conmeds in the class L04 IMMUNOSUPPRESSANTS that are also PDs with PD identifier COMD3.

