# 2.5 Analysis of the primary objective

# 2.5.1 Primary endpoint

The primary objective for the extension study is to assess safety of ZPL389. This is described in section 2.8. This section focuses on the primary objective of the core study which is to characterize the dose-response relationship of ZPL389 in subjects with moderate to severe AD assessed by IGA response after 16 weeks of treatment.

The primary clinical question of interest is: What is the effect of ZPL389 versus placebo on IGA response after the full 16 weeks of treatment in patients with moderate or severe atopic dermatitis, who do not use confounding therapy that may affect their AD or the assessment of it, regardless of their use of protocol-allowed concomitant medicatons?

This estimand will enable assessment of the effect of ZPL389 in the absence of confounding medication (such as rescue medication) and after the intended 16 weeks of treatment.

The primary estimand is described by the following attributes:

**Population:** Adult moderate to severe atopic dermatitis patients as defined by the study inclusion and exclusion criteria who were randomized to treatment, and not mis-randomized in the IRT. This implies that analyses will be based on the full analysis set.

**Endpoint:** IGA response at week 16, where IGA response is defined as an IGA score of 0 or 1 with at least a 2 point improvement compared to baseline and no use of confounding therapy before the assessment time point.

**Treatment of interest:** the randomized treatment (ZPL389 or placebo) plus medications as allowed by the protocol but with no further treatment for patients who discontinue study treatment due an AE or lack of efficacy.

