#### Handling of remaining intercurrent events:

- Use of confounding medication: set data after use of confounding medication to missing
- Treatment discontinuations for any reason: set data after discontinuation to be missing

The summary measure: difference in means between ZPL389 and placebo.

This estimand differs from that intended by the protocol in that the definition data recorded after the intercurrent events of use of confounding medication or treatment discontinuation are ignored in the analysis. The protocol had specified inclusion of all data as recorded regardless of use of confounding medication or discontinuation of treatment. This change was made to allow for an estimand for the analysis of dose-response for EASI that followed similar principles as that for the IGA response.

The following supportive estimand will also be considered to address the question of what would be the effect of ZPL389 versus placebo after treatment for up to 16 weeks and when confounding medication is allowed.

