# 2.6.8 Handling of missing values/censoring/discontinuations

Where data for a binary response endpoint are are missing, either because the underlying score was not recorded or because the response was set to missing as part of the handling of intercurrent events, the underlying score (IGA, or EASI) will be imputed using multiple impuation methods and the response derived from this imputed score.

The multiple imputation model will include scores from all visits from randomization up to the time point of imputation.

For endpoints that are analyzed as continuous variables (for example EASI score % change from baseline), missing values will not be imputed. In this cases the MMRM analysis approach is used to handle the missing data.

If a baseline value is missing and required to derive an endpoint, the baseline value will be imputed by the mean of the respective treatment group in the respective randomization stratum.

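### Missing IGA and EASI responses are imputed from the score alone, so confounding therapy after data end cannot count as failure and arm response rates tend to be overstated

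*SAP*

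**What the plan says.** SAP 2.5.1 defines the primary endpoint as IGA 0 or 1, at least 2 points of improvement from baseline, and "no use of confounding therapy before the assessment time point". The definition of confounding medications in SAP 2.1.1 is broad: "Any use of rescue medication or prohibited medication will be considerd as confounding therapy". SAP 2.5.1 adds that any such use is a non-response, replacing the protocol's adjudication. SAP 2.6.5 puts the same condition into EASI50 and EASI75 response.

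Treatment discontinuation for adverse event or lack of efficacy is a non-response under the primary estimand. Otherwise the rule is "Treatment discontinuations for any other reason: set data after discontinuation to be missing". For missing responses SAP 2.5.3 states that "the IGA score will be imputed using multiple impuation methods and the IGA response derived from this imputed IGA score", and "The multiple imputation model will include IGA categories from all visits from randomization up to Week 16". SAP 2.6.8 repeats this for the other binary endpoints: "the underlying score (IGA, or EASI) will be imputed using multiple impuation methods and the response derived from this imputed score". SAP 5.2.3 lists the remaining inputs: "The imputations will be done separately for each treatment group including baseline IGA, geographical region, baseline EASI score as additional covariates".

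For percent change in EASI, by contrast, SAP 2.6.2 has an explicit rule: "Use of confounding medication: set data after use of confounding medication to missing". No matching rule is stated for the scores behind the response endpoints.

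**The concern.** A patient with an observed Week 16 visit can fail in two ways: by score or by confounding therapy. For the period after data end, a patient whose Week 16 response is imputed can fail only by score. Followed as written, the method estimates the probability of a score response in imputed patients, whereas the endpoint is a score response without confounding therapy.

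The donor information has a related problem. Protocol 5.5.6 allows rescue after Week 4, and Table 5-1 lets study treatment continue after several prohibited therapies, so scores recorded on rescue will exist. If they enter the model, improvement due to rescue is passed on to patients with missing data.

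At stake are the reported response rates per arm and, to a lesser degree, the differences from placebo. The distortion grows with the share of patients imputed and with rescue use. SAP 2.5.4 (supportive estimand 3) notes that more patients than foreseen stopped by their own decision. These patients are imputed under the primary estimand.

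**Working it through.** **The plan's own figures.** The documents give no figure for imputation bias. The one related design figure, 90% power with 360 subjects at one-sided 2.5% (SAP 3), reproduces at a minimum power of 90.3% over the seven candidate shapes in protocol 9.4.2. The calculation used the logit scale, 10% on placebo and 30% at the maximum. It shows that the design inputs were read correctly and does not bear on the bias.

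**Inputs.** From the documents: discontinuation of 15% to 25% for all reasons (SAP 1.1), rescue only after Week 4, and imputation within arm under a normal model (SAP 5.2.3). Assumed, because the documents are silent: the rescue rate, the share of rescued patients who still score 0 or 1, and the share of patients imputed. The last of these is below the all-reason discontinuation rate to the extent that adverse-event and lack-of-efficacy discontinuations are not imputed.

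**Closed form.** Let m be the share of an arm that is imputed, u the share of those patients using confounding therapy that is not counted, and c the share of those users scoring 0 or 1. The excess in the arm's rate is m × u × c, which cannot be negative.

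- Low end: 0.05 × 0.10 × 0.10 = 0.0005, or 0.05 points.
- Middle: 0.15 × 0.20 × 0.25 = 0.0075, or 0.75 points.
- High end: 0.25 × 0.40 × 0.40 = 0.04, or 4.0 points.

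If confounding therapy recorded before data end counts as failure, only later use belongs in u, so these are upper figures for a given total use.

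For the difference from placebo, the bias is m × c × (u active - u placebo). With 20% active, 40% placebo and c = 0.25:

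- m = 0.05: 0.05 × 0.25 × (-0.20) = -0.25 points.
- m = 0.25: 0.25 × 0.25 × (-0.20) = -1.25 points.

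**Simulation.** Each of 16 scenarios had 20,000 patients, drop-out at random given observed data, and normal-model imputation of the IGA score (sequential regression and 5 imputations, in place of the SAP's MCMC and 100). The four corner scenarios, in percent:

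| Arm type | Drop-out | Rescue | Rescue and score 0/1 | True composite | SAP rule, recorded rescue kept as failure | SAP rule, score only | Composite imputed |
|---|---|---|---|---|---|---|---|
| Placebo-like, low | 15.0 | 11.2 | 1.9 | 18.0 | 18.2 | 18.2 | 17.9 |
| Placebo-like, high | 28.7 | 24.6 | 9.5 | 17.6 | 19.4 | 20.0 | 17.7 |
| Active-like, low | 14.1 | 8.0 | 2.4 | 35.0 | 35.1 | 35.2 | 34.8 |
| Active-like, high | 26.4 | 17.9 | 9.4 | 33.4 | 35.0 | 35.5 | 33.6 |

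Over all 16 scenarios the excess is 0.1 to 1.8 points if recorded rescue still counts as failure, and 0.2 to 2.4 points if it does not. Imputing the composite is within about 0.4 points of the truth throughout. The closed form agrees roughly: for placebo-like, high, 0.287 × 9.5 = 2.7 points against 20.0 - 17.6 = 2.4 simulated.

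Differences from placebo under the score-only rule:

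- Low corner: true 35.0 - 18.0 = 17.0; SAP rule 35.2 - 18.2 = 17.0; bias 0.
- High corner: true 33.4 - 17.6 = 15.8; SAP rule 35.5 - 20.0 = 15.5; bias -0.3.

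A single simulated rate of 18% has standard error √(0.18 × 0.82 / 20,000) = 0.27 points. The comparisons use the same patients, so their error is smaller, but figures of 0.1 to 0.3 points should be read as close to zero.

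**Scale.** At 90 per arm with 10% and 30%, the standard error of the difference is √(0.09/90 + 0.21/90) = 5.8 points. A bias of -1.25 points is about 0.2 standard errors; -0.3 is about 0.05.

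**The case against.** A reader might infer that an imputed patient can never fail by rescue. The documents do not support that. Confounding therapy recorded before drop-out is a non-response by the endpoint definition. Only use that would have come after data end is lost. The SAP does not, however, state that the definition takes precedence over imputation.

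Nor is it stated outright that scores recorded on rescue feed the model. That is inferred from the inclusion of every visit and the lack of any exclusion. The example code for deriving response in SAP 5.2.3 does not appear in the available text and may carry a rescue flag. Even so, such a flag could reflect only recorded use.

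The best counter-argument concerns the target. SAP 2.5.1 also describes the aim as the effect without confounding medication. Under that reading, imputing a rescue-free outcome for a patient set to missing is defensible. But the imputation should then not learn from scores recorded on rescue, and nothing removes them. The mismatch changes form but remains. The figures above are for the composite reading only.

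Three further points stand. The rescue rates are assumed. The bias largely cancels in the difference if the drug has no effect and rescue and drop-out are similar across arms. Supportive estimand 3 keeps the composite endpoint and makes every treatment discontinuer a non-responder, so only unrecorded assessments in other patients are imputed. The protocol's own imputation (9.4.3) also lacks a rescue component, so the SAP did not introduce the gap. Its move to unadjudicated use does widen the set of therapies that count.

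**Conclusion.** For the primary estimand, supportive estimand 1 and their EASI50/75 counterparts, the stated imputation does not match the endpoint. It tends to overstate arm response rates: by roughly 0.1 to 2.4 points in simulation and up to 4 points in closed form. Both ranges depend on assumed rescue use, response on rescue and share imputed. The effect on the difference from placebo is about 0 to -1.3 points, towards the null if placebo patients use more rescue.

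A reader might infer that the treatment comparison, or the decision to stop for lack of efficacy, is unsafe. The documents do not support that. The bias is small against a standard error of about 5.8 points at the planned size, and supportive estimand 3 gives a check that is mostly free of it. The SAP also reports that handling of confounding medication did not alter the interim conclusions, although that statement does not address the imputation model. The rule should be corrected because the arm rates will be reported and the correction is cheap.

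**What to change.** For the primary estimand, supportive estimand 1 and EASI50/75 under the same estimands:

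1. State that confounding therapy recorded before data end is a non-response and takes precedence over imputation.
2. In the imputation input, code visits after confounding therapy as non-response instead of using the score recorded there.
3. Impute the Week 16 composite response with a sparse logistic model, for example baseline IGA and last available responder status. Name a fallback in case of separation: fewer predictors, or pooled arms with a treatment term.

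If the sponsor instead intends the rescue-free target for patients set to missing, say so, and set scores after confounding therapy to missing in the imputation input, as SAP 2.6.2 does for percent change in EASI. Keep score-only imputation for supportive estimand 2, where confounding therapy is ignored.

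The cost is one derived input variable and a changed imputation step, with no new data. The price is fewer predictors in the small arms: 45 patients at 10% response gives 45 × 0.10 = 4.5 responders, fewer after early stopping, and SAP 5.2.2 already warns of non-convergence at low rates.
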